**University of Maryland, Shock Trauma Center
Department of Orthopaedics**

**Impact of Surgery on Pain in Lateral Compression Type Pelvic Fractures:
A Prospective Trial (Pelvis RCT)**

NCT02605766

University of Maryland IRB Number: HP-00060038

Principal Investigator: [name]

Safety Monitor: [name]

Version 4

June 1, 2016

TABLE OF CONTENTS

Protocol Summary	3
Key Roles.....	4
Background Information.....	4
Rationale	5
Potential Risks	5
Potential Benefits	6
Primary Outcome	6
Secondary Outcomes	6
Exploratory Outcomes	6
Description of the Study Design	6
Primary Endpoint	7
Secondary Endpoints	8
Study Population	10
Adjudicating Eligibility	11
Co-Enrollment Guidelines	11
Recruitment.....	11
Study Treatments	11
Clinical Evaluation.....	12
Participant Interviews	13
Study Schedule.....	13
Assessment of Safety	15
Data Analysis	16
Randomization	17
Data Management.....	17
Missing Data	18
Research Ethics Approval.....	18
Informed Consent.....	19
Vulnerable Populations.....	20
Participant Confidentiality	20
Study Discontinuation.....	21
Reports	21
Study Records Retention.....	21
Supporting Literature	21
APPENDIX A	23
APPENDIX B	23
APPENDIX C	See Attachements
APPENDIX D	See Attachements

PROTOCOL SUMMARY

Title	Impact of surgery on pain in lateral compression type pelvic fractures: a prospective trial
Short Title	Pelvis RCT
Type of Study	Prospective randomized control trial OR observational outcomes study
Primary Objective	To determine if surgical stabilization of lateral compression type pelvic fractures decreases patient reported pain at 2 weeks post injury compared to non-operative management.
Secondary Objective	To explore associations between treatment and: 
 1. Patient reported pain up to 1 year post injury 2. Hospital length of stay 3. Time to first mobilization (bed to chair) 4. Narcotic use up to 1 year post injury 5. Work productivity & activity impairment up to 1 year post injury 6. Health related quality of life up to 1 year post injury 7. Pelvic specific functional outcome up to 1 year post injury 8. General function up to 1 year post injury
Sample Size	We will recruit a sample size of 130 patients (65 per arm) with a minimum of 2 week follow-up for the primary outcome
Diagnosis and Main Inclusion Criteria	Lateral compression type pelvic fracture amendable to both operative or non-operative treatment per surgeon opinion in patients between the ages of 18 and 80 years of age, inclusive.
Length of Follow-up	1 year

Study duration: We will recruit for a year and a half. Patients will be followed for 1 year. We estimate 4 years total.

Primary outcome measure: *Pain* as measured by using the arithmetic mean of the four pain severity items on the patient-reported Brief Pain Inventory assessment (BPI) 2-weeks following the patient's injury.

Secondary outcome measures: *Length of stay* will be determined by recording the admission date versus discharge date for the patient's index hospitalization. *Time to first mobilization (bed to chair)* will be determined using the physical therapy notes during the patient's index hospitalization and is defined as days post-injury and days post-operative treatment (if applicable) to time of first mobilization (bed to chair). *Narcotic use* will be determined by cross-referencing the patient's medical record during the index hospitalization and follow-up clinic appointments with patient-reported usage. *Work productivity and impairment* will be determined using the modified WPAI:SHP questionnaire. *Health related quality of life* will be measured using the VR-12 questionnaire. *Pelvic function* will be measured using the Majeed Pelvic Score.

Statistical analysis: We are interested in estimating the causal effect of operative treatment versus non-operative treatment in lateral compression type pelvic fracture patients. For all our

analyses, we will report estimates of the causal effects, standard errors, and confidence intervals. We will also report the results of tests of null hypothesis of no causal effect.

KEY ROLES

Safety Monitor- [name] will be responsible for overseeing patient safety for the study. [name] will review the enrollment numbers and medical compliance annually for the duration of the study.

Coordinating Center Principle & Sub-Investigators- [name] [name] (PI) and the sub-investigators will be responsible for developing a detailed study protocol, providing oversight on study progress and act to correct deficiencies in the conduct of the study. The PI and sub-investigators will also draft the main publications related to the study, and assist with patient consent.

Site Principle & Sub-Investigators- The site PI and sub-investigators will be responsible for oversight on local study progress. The site PI and sub-investigators will also contribute to the main publications related to the study, and assist with patient consent.

Coordinating Center Research Coordinator- [name], research specialist, is responsible for maintaining all study documentation, developing and maintaining the master IRB application and consent, circulating any changes to study documents including protocols, case report forms, and IRB materials to the research team members and site research coordinators, providing daily oversight and management of study implementation, performing data quality control and analysis of study results. The coordinating center research coordinator will also conduct monthly reports for each site.

Site Research Coordinator- The site research coordinator is responsible for communicating any problems or concerns with the coordinating center, maintaining all local study documentation, developing and maintaining the site IRB application and consent, and circulating any changes to study documents including protocols, case report forms, and IRB materials to the site research team members.

Research Team Members- The research team members are responsible for the conduct of the clinical study including patient enrollment, performing study procedures, data collection and conducting study follow-up visits.

BACKGROUND INFORMATION

Lateral compression type pelvic ring injuries remain the most common type of pelvic fractures encountered. There is a substantial amount of controversy surrounding the treatment of these injuries and there is evidence that both operative and non-operative treatment can be successful. The crux of the problem is determining which of these patients would benefit from early surgical stabilization and which will heal uneventfully without surgery. Many authors site patient pain

and inability to mobilize as indications for surgery, although there is conflicting evidence supporting this claim. The presence of chronic pain in the trauma population is a growing area of interest, and there is a push towards controlling pain more effectively in the acute setting. It remains to be proven that surgical intervention is more effective at decreasing acute and longer term pain.

RATIONALE

There is evidence in the literature to support both operative and non-operative treatment of patients with LC1 or LC2 pelvic fractures. There is conflicting evidence that surgical stabilization decreases acute pain and narcotic requirements, although patients are often counseled to that effect. We propose to prospectively randomize patients with lateral compression type pelvic fractures to non-operative versus operative treatment and track which group has less pain, less need for narcotic pain medications, and who mobilizes with physical therapy faster.

POTENTIAL RISKS

If the patient is randomized to operative treatment, he/she will be exposed to all of the risks associated with surgery under a general anesthetic including but not limited to: prolonged intubation, heart attack, stroke and death. These risks are extremely rare and will be explained to the patient and/or family by the anesthesia team, and a separate anesthesia consent will be obtained. The risks of the surgical procedure are rare but include: infection, wound break down, failure of hardware, and neurologic injury. A separate surgical consent will be provided to go into more detail of the risks of the procedure.

The risk of non-operative treatment is displacement of fracture with possible need for surgical intervention or prolonged protected weight-bearing. This is unlikely but will be monitored closely, as per our standard of care.

While the intake questionnaire and information gathered is of a sensitive nature (income, narcotic use, pain and psychiatric history) and it might cause the patient some discomfort to answer truthfully, all information will be kept confidential and no identifiers will be used in publication.

While every attempt will be made to keep all information confidential and the master link between the patient study number and personal identifiers will be destroyed at the completion of the study, there remains a risk of the potential for the loss/breach of confidentiality. This risk will be minimized by storing all paper questionnaires in a secure, locked location and all electronic data will be password protected.

There may be risks in this study which are not yet known.

POTENTIAL BENEFITS

While there are no direct benefits to patients participating in the study (except for those that may accrue from closer clinical observation as a study patient), participation may help determine the best treatment for lateral compression type pelvic fractures in the future.

PRIMARY OBJECTIVE

To compare 2-week post-injury assessments of patient reported pain of participants undergoing operative versus non-operative treatment following a lateral compression type pelvic fracture. We hypothesize that there will be a decrease in the Visual Analog Scale (VAS) pain scores in the operative group as compared to the non-operative group both during their hospital stay and in the short-term outpatient follow up.

SECONDARY OBJECTIVES

To compare assessments of narcotic use up to 1 year post injury of participants undergoing operative versus non-operative treatment following a lateral compression type pelvic fracture. We hypothesize that there will be a decrease in the narcotic requirements in the operative group as compared to the non-operative group throughout the 1 year follow up.

To compare assessments of time to first mobilization (bed to chair) with physical therapy of participants undergoing operative versus non-operative treatment following a lateral compression type pelvic fracture. We hypothesize that the operative group will mobilize out of bed to chair with physical therapy faster than the non-operative group.

EXPLORATORY OBJECTIVES

To explore associations between treatment and:

1. Hospital length of stay (index hospitalization)
2. Work productivity and activity impairment up to 1 year post injury
3. Health related quality of life up to 1 year post injury
4. Pelvic specific functional outcome up to 1 year post injury.

DESCRIPTION OF THE STUDY DESIGN

The Pelvis RCT study is a prospective randomized treatment trial to evaluate outcomes among operative versus non-operative lateral compression type fractures. If the patient does not agree to randomization, the patient will be asked to participate in the observational arm of the study. A schematic representation of participant enrollment can be found in the figure below.

A total of 130 patients will be enrolled (65 per arm). University of Maryland, Shock Trauma Center will act as the coordinating center for this study and all patient will be recruited from

University of Maryland, Shock Trauma Center and Indiana University Health Methodist Hospital.

Patients and/or the patient's legally authorized representative (LAR) will be approached for informed consent as soon as is feasible following determination of eligibility.

During the index hospitalization, participants will be asked to provide basic demographic information, health status and function prior to injury. Study injury characteristics will be obtained from the surgeon and the participant's medical record.

Participants will be prospectively followed at 2 weeks, 6 weeks, 3 months and 1 year post-injury. All follow-ups will occur in person at the hospital clinic follow-ups or over the phone and will consist of both a clinical examination (when applicable) and interview.

[figure not shown]

Figure: Participant Enrollment

PRIMARY ENDPOINT

The primary endpoint is *patient reported pain severity* as measured by the Brief Pain Inventory assessment (BPI). The BPI is a 15-item questionnaire that assesses the severity of pain, the impact of pain on daily function, the location of pain, pain medications and the amount of pain relief. There is no scoring algorithm but the arithmetic mean of the four severity items can be used as a measure of pain severity and the arithmetic mean of the seven interference items can be used as a measure of pain interference. This assessment has been chosen because it is a short, reliable, patient reported assessment of pain that has been specifically designed for and validated in patients with pain from acute conditions such as postoperative pain.

SECONDARY ENDPOINTS

The secondary endpoints include:

1. *Length of stay.* This will be found in the patient's medical record using the admission date and time versus the discharge date and time during his/her index hospitalization.
2. *Time to first mobilization (bed to chair).* This will be found in the patient's medical record during his/her index hospitalization. Data will be found in the physical therapy notes and will be recorded as days post-injury and days post-operative treatment if applicable.
3. *Patient reported narcotic use.* This is will be recorded by cross-referencing the patient's medical record and patient-reported questionnaire about pain medication use. The total narcotic use will be converted to the morphine equivalent for statistical analysis.

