Our primary hypothesis is that the operative treatment group will have lower VAS pain scores compared to the non-operative treatment group both during their hospital stay and in the short-term outpatient follow-up.

Based on the results of a pilot study, we expect pain scores in the non-operative group to have a mean of 5.7 and a standard deviation of 2.3. Assuming a 20% reduction in pain scores, 130 patients (65 per arm) are required to have an 80% chance of detecting, as significant at the 5% level, a decrease in the primary outcome measure from 5.7 in the control group to 4.56 in the experimental group. This is our primary outcome and the study will be powered for this variable.

Primary data analysis will involve direct comparison of the change in value of the reported pain scores at the time points listed below. We will be powered to detect a 20% reduction in pain. Secondary analysis will compare the value of narcotics administered at the distinct time periods. Tertiary analysis will be comparing the time (in days) to mobilization with physical therapy. The previous retrospective pilot study incorporated a propensity factor, generated from well documented sources of pain. As this is a prospectively randomized trial, we do not anticipate needing to accommodate for matching.

RANDOMIZATION

Eligible patients will be randomized in equal proportions to one of the two treatment groups: 1) operative treatment of the lateral compression type fracture, 2) non-operative treatment of the lateral compression type fracture. Allocation will be concealed using a centralized 24-hour computerized randomization system, www.randomize.net, that will allow Internet based allocation. The treatment allocation will be stratified on the following prognostic factors to ensure balance between the intervention groups: 1) patient intubation status at time of enrollment, 2) patient prescription pain medication usage during the month prior to injury.

DATA MANAGEMENT

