**Pelvis RCT: Impact of Surgery on Pain in Lateral Compression Type Pelvic Fractures**

**NCT: 02625766**

**December 28, 2020**

### Statistical Analysis

[figure not shown]
The primary analyses were based on the intent-to-treat principle. The primary analysis for pain and secondary analysis for functional outcome estimated the difference in the average treatment effect based on a longitudinal assessment within the initial 12-weeks after the fracture. This approach uses each patient's multiple outcome assessments to compare the average pain and function experienced over the 12-week period between the treatment groups. For these analyses, we used a Bayesian hierarchical model that applied a prior probability of no treatment difference based on the conflicting evidence in the prior literature [3-6]. This is akin to an initial assumption that there is "no difference" in pain or functional outcome between the treatment groups. In addition to estimating the average treatment effect, we calculated the posterior probability (meaning conditioning the prior distribution on the data at hand) of treatment benefit with operative treatment under various minimally clinical important difference (MCID) thresholds. The models included a dummy variable for each patient as a random intercept, an autoregressive correlation structure, and adjusted for whether the treatment was randomly assigned, the patient's pre-injury narcotic use, and a time-varying covariate that measured narcotic use at each time point. Multivariable linear regression was used to analyze the treatment effect on hospital length of stay and time to mobilization. Outcome data were missing in 16% of the sample at 2-weeks, and 14% of the sample at 6-weeks and 12-weeks, and was therefore imputed using multiple imputation for the final models [16]. To assess possible effect measure modification based on the initial degree of displacement, we stratified the sample to create two subgroups, patients with  $\geq 5$ mm of displacement and patients with  $< 5$ mm of displacement. We then calculated the average effect of operative treatment on pain in each of the subgroups. In addition, we compared the average treatment effect of operative fixation on pain with posterior-only fixation compared to operative fixation with anterior and posterior fixation. Additional sensitivity analyses recalculated the pain and function outcomes to separately compare the treatment effects between patients enrolled in the randomized cohort and the observational cohort. The analyses were performed using R Version 3.6.1 (Vienna, Austria) with the packages *lme4*, *rstan*, *brms*, and *mice*.

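### The SAP describes no between-group analysis of narcotic use, no 1-year analysis of any outcome and no VR-12 or WPAI analysis, although the protocol lists all of these, and it gives no reason

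*Protocol*

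**What the plan says.** **Protocol.** The primary objective asks whether surgery "decreases patient reported pain at 2 weeks post injury compared to non-operative management". The Protocol Summary then lists eight secondary objectives, among them "Patient reported pain up to 1 year post injury" and "Narcotic use up to 1 year post injury".

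Narcotic use is developed furthest:
- It is the first objective under Secondary Objectives ("To compare assessments of narcotic use up to 1 year post injury"), with the hypothesis that requirements will be lower in the operative group throughout follow-up.
- Secondary Endpoints fixes its scale: "The total narcotic use will be converted to the morphine equivalent for statistical analysis".
- Data Analysis gives it a comparison: "Secondary analysis will compare the value of narcotics administered at the distinct time periods".

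Appendix B schedules the BPI, medication use, WPAI, VR-12 and Majeed score at 1 year.

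**SAP.** Under Statistical Analysis, pain and function are analysed in "a longitudinal assessment within the initial 12-weeks after the fracture". Narcotic use enters those models twice, both times for adjustment: once as pre-injury use and once as a time-varying covariate. Length of stay and time to mobilization are analysed by linear regression. Missing outcome data are reported at 2, 6 and 12 weeks only. VR-12 and WPAI are not mentioned.

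**The concern.** The two documents disagree about which outcomes are analysed and over what period. This is more than a missing detail: an analyst who follows the SAP as written produces no treatment comparison for a hypothesised secondary outcome and no estimate at the last scheduled visit.

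Three things are at stake.

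- **Persistence.** The protocol's Background says it is still unproven that surgery is better at reducing both acute and longer-term pain. An average over 12 weeks cannot speak to the longer-term part.
- **Reading the pain result.** Less need for narcotics is one of the aims in the Rationale. A pain difference means something different if analgesic use also differs between groups, so the two need to be reported together.
- **Traceability.** The SAP is written in the past tense with results in hand. If pre-stated outcomes and time points are absent without comment, a reader cannot tell a reasoned change from an unreasoned one.

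**Working it through.** The point rests on comparing the documents, not on a sample-size figure. For completeness, the protocol's own number reproduces. The difference is 0.20 × 5.7 = 1.14, with SD 2.3, a two-sided 5% level and 80% power. The normal approximation n = 2(1.96 + 0.84)² × 2.3² / 1.14² gives 64 per arm after rounding up. The t-test version gives 64.87, so 65 per arm and 130 in total, as stated. That calculation concerns the primary pain outcome, and nothing below alters it.

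**Protocol Summary objectives against the SAP**

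| Secondary objective | Horizon in protocol | Analysis in SAP |
|---|---|---|
| Pain (BPI) | 1 year | To 12 weeks only |
| Length of stay | Index stay | Yes |
| Time to first mobilization | Index stay | Yes |
| Narcotic use | 1 year | None as an outcome; covariate only |
| Work productivity (WPAI) | 1 year | None |
| Quality of life (VR-12) | 1 year | None |
| Pelvic function (Majeed) | 1 year | To 12 weeks only |
| General function | 1 year | None |

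The counts are 2 of 8 fully covered, 2 of 8 covered to 12 weeks, and 4 of 8 with no analysis (2 + 2 + 4 = 8). Six of the eight run to 1 year, and 0 of those 6 has a 1-year analysis.

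**The shorter list.** Secondary Endpoints numbers six endpoints and leaves out pain and general function. Three have an SAP analysis (length of stay, mobilization, and Majeed to 12 weeks). Three have none (narcotic use, WPAI, VR-12).

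**Visits.** Appendix B gives the BPI five post-injury assessments (96 hours, 2 weeks, 6 weeks, 3 months, 1 year). Post-injury medication use, WPAI, VR-12 and Majeed have four. In each case the 1-year assessment lies outside the SAP's window. Length of stay and mobilization have no 1-year measurement, so the point does not apply to them.

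**Narcotic use as a covariate.** The protocol hypothesises that treatment lowers narcotic use. On that hypothesis, post-injury narcotic use is a consequence of treatment. Adjusting for it leaves the narcotic question without an analysis. It also changes the pain estimate from the overall effect of treatment to an effect at a given level of narcotic use. The documents give no figure from which the direction or size of that change could be worked out.

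**WPAI scoring.** The overall-impairment formula printed under Secondary Endpoints is (b/(b + d) + [1 + (b/(b + d)) × (e/10)]) × 100. A patient who missed no hours and had no impairment at work has b = 0 and e = 0. The formula then gives (0 + [1 + 0 × 0]) × 100 = 100%, which is full impairment. It must be checked before WPAI is analysed.

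**The case against.** Four objections have force.

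1. **The SAP file is a methods supplement to an article that is not available here.** A reader might infer that the narcotic hypothesis was never tested, that the 1-year questions went unanswered, or that outcomes were reported selectively. The documents support none of these. They show only that the SAP describes no such analysis and does not say why.

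2. **The protocol's main question is short-term.** A reader might take 1 year as the horizon of the whole trial. It is not: the primary objective is at 2 weeks, and two secondary outcomes end with the index stay. For pain, the 1-year horizon comes from the summary list, which is framed as exploring associations. Secondary Objectives contains no 1-year pain objective, and the pain hypothesis covers the hospital stay and early outpatient follow-up, which a 12-week window arguably fits. This weakens the pain limb but does not remove it, because the summary states the objective and the BPI is scheduled at 1 year.

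3. **The missing outcomes do not rank equally.** Exploratory Objectives includes work productivity, quality of life and pelvic function, while the Protocol Summary and Secondary Endpoints call them secondary. Missing models for VR-12 and WPAI therefore weigh less than the missing narcotic analysis.

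4. **The 1-year data may be thin.** The documents show that the visit was scheduled, not how complete it was. That is a reason to report completeness, not to leave the visit out without comment.

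**Conclusion.** The inconsistency is real and should be resolved. It is strongest for narcotic use, which has an objective, a directional hypothesis, a unit of measurement and a planned comparison in the protocol, yet appears in the SAP only as an adjustment variable. It is moderate for 1-year pain and function, which the SAP covers to 12 weeks. It is weakest for VR-12 and WPAI, given their exploratory label in one part of the protocol. In size, none of the six summary objectives running to 1 year has a 1-year analysis, and four of the eight have none at any time.

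This conclusion rests on the text of the two documents and assumes that the SAP file is the whole analysis plan. The primary 2-week objective and the sample size are not affected by it.

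**What to change.** 1. Analyse narcotic use in morphine equivalents as an outcome, by visit, through 1 year.
2. Add the 1-year visit to the BPI and Majeed models with a treatment-by-visit contrast at 1 year. Leave post-injury narcotic use out of these models, because treatment may affect it.
3. Analyse VR-12 and WPAI by visit and label them exploratory. Choose a model suited to each score: the WPAI work scores depend on employment and hours worked. Check the printed overall-impairment formula first.
4. Report 1-year completeness and apply the sensitivity framework in the protocol's Missing Data section. For any outcome or time point that was dropped, general function included, state when and why.

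The cost is further analysis of assessments the protocol already scheduled, with no new patients. The 1-year results may have more missing data and wider intervals. Since the SAP already contains results, the added analyses should be marked as late additions to the SAP for outcomes named in the protocol.
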